7.5 Description of HF

Summary statistics will be provided for the variables described in the subsections *Clinical features*, [REDACTED] and *Diagnostic and therapeutic procedures* of Section 6.2 and Section 6.3. In detail, the following patient sets will be used for these analyses ([Table 7-1](#)):

Table 7-1 Analysis of HF

Variables from sub-section	Patient sets and stratifications used for analysis
----------------------------	----------------------------------------------------

Clinical features (Visit 1)	
 Enrolled Set (all patients from Enrolled Set and additionally stratified by inclusion in prospective period of the study)
Clinical features (Visit 2 and 3)	
 Follow-up Set
Diagnostic and therapeutic procedures	
 Follow-up Set

The following definitions will be applied for derived variables:

- The duration of HF will be calculated as *(date of V1 - 1 July in year of first HF diagnosis)/365.25*. If this calculation leads to a negative value, the duration will be set to 1/365.25.
- In addition, the duration of HF disease will be provided in categories (> 3 years, \leq 3 years). In case the duration of HF is missing, the approximate duration of HF reported in the eCRF will be used.

The number of hospitalizations due to HF will be provided for the patients with any hospitalization due to HF prior to the respective visit. The same algorithm will be applied for the number of emergency room visits due to HF and the number of visits in HF outpatient clinic or cardiologist.

For variables with category “Other”, any specifications reported will be listed.

7.6 NT-proBNP

NT-proBNP will be analysed at Visit 1 for the Enrolled Set, stratified by inclusion into the prospective period of the study, and at Visit 1 and Visit 3 for the Follow-up Set, and additionally stratified by adherence to ESC guidelines before and after referral to cardiologist.

Summary statistics for NT-proBNP at Visit 1, Visit 3 and the absolute change from Visit 1 to Visit 3 will be provided. In case an interval is given for the NT-proBNP result, the following rules will be applied: if the value is estimated downwards (i.e. “ $<$ XX pg/ml”), the new value XX-1 pg/ml will be used for the analysis. If the value is estimated upwards (i.e. “ $>$ XX pg/ml”), the new value XX+1 pg/ml will be used for the analysis.

In addition, NT-proBNP in groups (\geq 600 to $<$ 800 pg/ml, \geq 800 to $<$ 1000 pg/ml, \geq 1000 to $<$ 1200 pg/ml, \geq 1200 pg/ml to $<$ 1400 pg/ml, \geq 1400 pg/ml to $<$ 1600 pg/ml, \geq 1600 pg/ml to $<$ 1800 pg/ml, \geq 1800 pg/ml to $<$ 2000 pg/ml, \geq 2000 pg/ml) will be displayed by visit.

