To assess in clinically stable patients the impact of patients' key baseline characteristics on the cardiologists' and primary care physicians' prescription practice for HF treatment and the adherence of these treatment choices to the recommendations of the current ESC guidelines.	
Title: Proportion of clinically stable patients for whom the cardiologist and/or primary care physician optimizes treatment (i.e. prescribes a treatment regimen adherent to ESC guideline recommendations) post referral, stratified according to key baseline characteristics
 
Description: For patients who enter the prospective period of the study the post-referral treatment choice of cardiologists and/or primary care physicians will be documented; for patients, for whom the cardiologist and/or primary care physician chose to prescribe a novel HF treatment, the treatment will be assessed, if it fulfills the definition of adherent to ESC guideline recommendation. The proportion of patients for whom an ESC guideline adherent treatment was de novo prescribed will be assessed stratified according to anamnestic (e.g. duration of HF, previous treatment of HF, presence of cardiovascular/ metabolic/ pulmonary comorbidities), demographic (e.g. sex, race, smoking status) and NT-proBNP level categories (e.g. 600 -799 pg/ml, 800 – 999 pg/ml, 1000 – 1200 pg/ml, > 1200 pg/ml).
 
Units: Absolute and relative frequency distributions.
 
Time frame: Visit 2 and Visit 3
	Section 9.3
To describe the blood levels of NT-proBNP in CHF patients managed in the primary care setting	
Title: NT-proBNP
 
Description: NT-proBNP levels (pg/ml) will be measured at baseline in all consecutive patients who satisfy the inclusion and exclusion criteria. Measurements are performed on-site by means of a handheld device provided for the purposes of the study.
 
Units: Descriptive statistics for quantitative data, absolute and relative frequency distributions in clinically stable and unstable CHF patients
	Section 9.5.3

OBJECTIVE	Endpoint Title, Description and Reporting Time Frame for analysis and Unit of Measure	Stat Analysis Section
	Time frame: One measurement in all consecutive patients at baseline (Visit 1)	

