3.1 Study design

This is an international, prospective, low-interventional study enrolling patients with chronic heart failure with reduced ejection fraction (LVEF \leq 40%) who are managed in the primary care setting across Europe. The study comprises three visits over a period of maximum 10 months. Enrollment is planned to last 24 months.

At baseline (**visit 1**) for all consecutive patients, who satisfy the inclusion and exclusion criteria, the demographic and clinical characteristics, their current therapy regimen for the treatment of HF, any concomitant medication and their baseline QoL (EQ-5D and KCCQ questionnaires) will be documented. At this visit, after the investigator documents his/her decision whether the patient is considered being clinically stable*, all patients (clinically stable and not stable) will have a blood test for assessing NT-proBNP levels.

[figure not shown]
Only patients who are considered being clinically stable* by the investigator and who show NT-proBNP blood levels \geq 600 pg/ml will enter the prospective period of the study.

Patients, who do not fulfill these criteria, i.e. are either not meeting the above definition of clinical stability or who show NT-proBNP levels $<$ 600 pg/ml will not continue further into the study and will have their end-of study documentation at the baseline visit.

Clinically stable patients with NT-proBNP levels \geq 600 pg/ml will be referred to a cardiologist for evaluation of their HF treatment. After the referral visit to the specialist's office, the patient will return within a suggested time window of up to 4 weeks after the cardiologist visit to the primary care physician for **visit 2**. During visit 2 the primary care physician will evaluate and record the recommendations provided or treatment changes introduced by the specialist and will make and record his/her decision on the patient's future HF treatment. There is no minimal visit time window for the timing of visit 2, as referral policies differ between different European countries and healthcare systems. However, visit 2 should be performed no later than 6 months after the baseline visit. Within this time frame, the exact timing will be managed by the primary care physician according to his/her practice and local organizational models.

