3.6 Risks and benefits

The risk to subjects in this trial will be minimized by compliance to the eligibility criteria. Blood sampling for NT-proBNP measurements will be performed at the baseline visit and at Visit 3 (for patients who enter the prospective period of the study), which bears minimal risks for the patient, associated with the sampling procedure (venous puncture). Other study procedures are observational, i.e. the investigators should follow and document their local clinical routine for the treatment and follow-up of patients with CHF. There is no investigational medicinal product and no drug/device treatment that is required by the protocol. Therefore the risks associated to this study, besides those associated to the venous blood sampling procedure, are comparable to those in a usual primary care setting.

4 Population

The study population will consist of adult (≥ 18 years) male and female patients with chronic heart failure with reduced ejection fraction (LVEF $\leq 40\%$) who are currently managed in a primary care setting in sites across Europe. Provided the below inclusion and exclusion

criteria are met, all consecutive CHF patients at a given site will be documented and will be subject to NT-proBNP measurement at baseline. Prior to measuring NT-proBNP at baseline, the physician must provide his/her judgement, whether the patient is considered as clinically stable based on the definition provided in [Section 2.1](#). Patients who do not meet the definition of being clinically stable at baseline and/or patients who show NT-proBNP levels < 600 pg/ml at baseline will not enter the prospective period of the study, but their baseline information will be documented. Patients who enter the prospective period of the study, as defined as clinically stable patients with NT-proBNP levels \geq 600 pg/ml will be referred to a cardiologist and will return to the site 2 more times (Visit 2 and Visit 3) for follow-up documentation.

It is planned to enroll a total of 4,000 CHF patients of which approximately 2,400 are estimated to enter the prospective period (are considered clinically stable and show NT-proBNP levels \geq 600 pg/ml). The recruitment will be regarded as completed once approximately 2,400 patients have entered the prospective period irrespectively how many patients have been enrolled totally.

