7.1 General methodology

In general, descriptive statistical analyses will be performed. If not described differently, analyses at Baseline will be performed for all patients in the Enrolled Set and additionally stratified by inclusion into the prospective period of the study (Yes, No). Analyses regarding the prospective period of the study will be carried out in the Follow-up Set. In specific cases, analysis in the Follow-up Set will be additionally stratified by adherence to ESC guidelines before and after referral to cardiologist (ESC non-conform/ESC conform, ESC non-conform/ESC non-conform, ESC conform/ESC conform, ESC conform/ESC non-conform, details are specified below). All subgroup analyses are described below in [Section 7.10](#).

Quantitative data (e.g. age) will be analysed by the statistical parameters valid N, missing N, mean, standard deviation, minimum (0%), median (50%), and maximum (100%).

Qualitative data (e.g. gender) will be presented by means of (absolute and relative) frequency distributions. The calculation of percentages will be based on the observed data per parameter, excluding patients with missing values (exceptions are described below). Exact Clopper-Pearson 95%-confidence intervals (CIs) will be calculated if applicable (see descriptions below).

Analyses of conditional endpoints (e.g. amount of cigarettes consumption in pack years) will be based on the number of subjects fulfilling the respective condition (e.g. patients with current or former consumption of cigarettes).

If indicated by the data, results of statistical analysis may be complemented by individual patient listings.

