7.4.2 Adherence to ESC guidelines (primary analysis)

For each patient, HF treatment at every visit will be classified with respect to adherence to ESC guidelines on level 1 and level 2 as outlined in [Section 4.5.1](#). Respective frequency distributions of adherence (yes, no) will be provided for the Follow-up Set for every visit.

The primary analysis will be performed on guideline adherence level 1 (as described in [Section 4.5.1](#)) as follows: based on the patients in the Follow-up Set treated not according to ESC guidelines at Visit 1, absolute and relative frequencies of A2 will be provided. The proportions within this analysis will be calculated twice, with and without considering missing values for A2. 95%-CIs will be provided for the proportions.

This analysis of A2 will be repeated for all patients in the Follow-up Set treated according to guidelines (level 1) at Visit 1.

For sensitivity, the analyses of A2 conditional to guideline adherence at Visit 1 will be repeated for guideline adherence level 2 (drug type and dose).

For the Enrolled Set, adherence to ESC guidelines (level 1 and level 2) will be analysed at Visit 1, additionally stratified by inclusion into the prospective period of the study.

In addition, the analyses of guideline adherence with respect to drug type will be repeated without taking into account the indication of the applied medications. This means, patients taking an ACEi, ARB, Beta-Blocker or MRA without HF indication will not automatically be classified as non-adherent in this analysis. Instead, these drugs will be included in the analysis and can contribute to a guideline adherent treatment of the patient.

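### The baseline NT-proBNP display by clinical stability that protocol Table 2-1 specifies is not planned in the SAP, and the split by prospective entry cannot stand in for it

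*SAP*

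**What the plan says.** For the secondary objective on NT-proBNP levels in primary care, protocol section 2.4 (Table 2-1) gives the output as "Descriptive statistics for quantitative data, absolute and relative frequency distributions in clinically stable and unstable CHF patients", measured once at Visit 1.

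The SAP plans the following:

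- Section 7.6: "NT-proBNP will be analysed at Visit 1 for the Enrolled Set, stratified by inclusion into the prospective period of the study". The Follow-up Set is then shown at Visits 1 and 3 and split by guideline adherence before and after referral.
- Section 7.1, the default for baseline analyses: "all patients in the Enrolled Set and additionally stratified by inclusion into the prospective period of the study". The overall Enrolled Set result is therefore shown as well.
- Section 7.6 categories: eight bands, the lowest starting at 600 pg/ml.
- Section 7.2: unstratified one-way counts of NT-proBNP below or at/above 600, of clinical stability, and of suitability for the prospective period.
- Section 7.11: subgroup analyses of other outcomes; stability is not among the subgroups.
- Section 7.13: three declared deviations from the protocol, none of them this one, although section 2.5 states that the SAP is consistent with the protocol.

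On entry, protocol section 3.1 ends participation at baseline for patients who "are either not meeting the above definition of clinical stability or who show NT-proBNP levels" under 600 pg/ml. The Population section (section 4) repeats that "patients who show NT-proBNP levels < 600 pg/ml at baseline will not enter the prospective period of the study".

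**The concern.** The SAP's grouping variable is partly defined by the variable being summarised. The group that enters the prospective period contains only stable patients at or above 600 pg/ml. The group that does not enter pools stable patients below 600 with unstable patients at any level. Neither column describes stable patients or unstable patients.

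Two things are at stake. A display that the protocol specifies for a secondary endpoint would not be produced, without being declared. The contrast that is produced will also show much higher NT-proBNP in the entry group whatever the true relation between stability and NT-proBNP, so it says little about that relation.

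**Working it through.** **1. Is the display planned anywhere else?** Table 2-1 asks for two groups, stable and unstable. SAP 7.6 and 7.1 give the overall Enrolled Set and entry yes/no. SAP 7.2 gives margins only, and 7.11 does not use stability. SAP 6.2 lists stability as a variable, but no visible section crosses it with NT-proBNP. Some SAP text is redacted (section 6.3 and part of 7.5), so this rests on the visible text. Section 7.6, the dedicated NT-proBNP section, is visible.

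**2. The plan's own numbers (protocol 9.8).** 2,160 / 0.60 = 3,600; 3,600 / 0.90 = 4,000; 4,000 × 0.60 = 2,400 entering. These reproduce. The 60% is the share of all patients at or above 600, so 2,400 / (4,000 × 0.60) = 1.00: the chain implicitly treats every patient as stable. It supplies no stable share to use here. SAP 4.2 also records that the study was stopped early, so the planned totals serve only as illustration.

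**3. Who is in the non-entry group?** Let s be the stable share (an assumption; the documents give none), with 60% at or above 600 in both stable and unstable patients. The unstable share of the non-entry group is (1 − s) / (1 − 0.60s):

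- s = 0.60: 0.40 / 0.64 = 62%
- s = 0.80: 0.20 / 0.52 = 38%
- s = 0.95: 0.05 / 0.43 = 12%

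Per 4,000 enrolled at s = 0.80, 4,000 × 0.80 × 0.60 = 1,920 enter. The other 2,080 are 1,280 stable patients below 600 and 800 unstable patients. The non-entry column is not an unstable column.

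**4. How far does the entry rule fix the contrast?** Assume a log-normal marker with log-SD 1.0, 60% at or above 600 overall, s = 0.80, and entry exactly as the rule states.

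With no true stable/unstable difference, the medians have a closed form:

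- Both true medians: 600 × exp(0.2533) = 773.
- Entry group (upper 60% of stable patients, so its median leaves 30% above it): 773 × exp(0.5244) ≈ 1,306.
- Non-entry group (52% of all patients; its median lies below 600, at the overall 26th percentile): 773 × exp(−0.6433) ≈ 406.

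Simulation of 1,000,000 patients per scenario agrees, and also covers the case where unstable patients truly have twice the level:

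| True unstable/stable ratio | Stable median | Unstable median | Entry median | Non-entry median |
|---|---|---|---|---|
| 1.0 | 773 | 772 | 1,304 | 406 |
| 2.0 | 682 | 1,360 | 1,238 | 426 |

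In the second row unstable patients have the higher levels, yet the entry column, which contains only stable patients, is the higher of the two.

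Over log-SD 0.8, 1.0, 1.2 and s = 0.60, 0.80, 0.95, the entry/non-entry ratio of geometric means is 2.2 to 6.0 with no true difference, and 1.7 to 5.6 when unstable patients are twice as high. The ranges overlap almost entirely, so the split hardly distinguishes the two situations.

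**5. What can be recovered from SAP 7.2?** If suitable means stable and at or above 600, and stability is recorded for all analysed patients (SAP section 5 already requires NT-proBNP):

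- share at or above 600 among stable = suitable / stable
- share at or above 600 among unstable = (N at or above 600 − suitable) / (N − stable)

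Means, medians, SDs and finer categories by stability cannot be recovered.

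**6. Categories.** The 7.6 bands give no place to Enrolled Set patients below 600. The only count of them is the overall two-way split in 7.2, so even the overall frequency distribution in 7.6 is incomplete.

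**The case against.** The strongest reply is that the SAP followed the protocol's analysis sections. The objective itself is to describe NT-proBNP in primary-care patients with no mention of stability, and the overall Enrolled Set summary does that. Protocol 9.2 prescribes the entry split for baseline characteristics. Table 2-1 refers this endpoint to protocol 9.5.3, which asks only for summary statistics by visit. Stability appears only in the units line of Table 2-1. The display is secondary and descriptive, in a study that SAP 7.12 calls exploratory, and part of it can be derived from the 7.2 counts.

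Much of this stands. The entry split is legitimate and should stay, and the overall objective is addressed. But the units line is the protocol's specification of the output, it names "absolute and relative frequency distributions in clinically stable and unstable CHF patients", and nothing in 9.2 or 9.5.3 withdraws it. The 7.2 counts yield one proportion per group, not the descriptive statistics specified.

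A reader might infer more than the documents support:

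- *That a formal stable-versus-unstable comparison was promised.* Table 2-1 promises description in both groups and no test or contrast.
- *That baseline adherence has the same defect.* SAP 7.4.2 does use the same split ("For the Enrolled Set, adherence to ESC guidelines (level 1 and level 2) will be analysed at Visit 1, additionally stratified by inclusion"), but the protocol specifies no adherence display by stability. Adherence is not part of the entry rule, so a yes/no difference there is not built in. It is only harder to interpret, because the non-entry group is mixed.
- *That the plan fails to test whether 600 pg/ml picks out under-treated stable patients.* No objective asks this. Protocol 3.2 describes the cut-off as arbitrary and uses it to select patients for follow-up.
- *That the entry column will be read as the stable patients.* Both documents define entry by stability and NT-proBNP together, and no column is labelled stable.

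**Conclusion.** The point holds for baseline NT-proBNP. A display specified in protocol Table 2-1 is absent from the visible SAP and undeclared in section 7.13, and the split by prospective entry cannot replace it because NT-proBNP is part of the entry rule. The bands in 7.6 also omit enrolled patients below 600.

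That entry truncates one group and mixes the other follows from the documents alone. The size does not: the 1,304 versus 406 pg/ml and the ratios of 1.7 to 6.0 depend on an assumed stable share and an assumed log-normal spread. They show direction and plausible order, and are not predictions for this study.

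The consequence is limited to one secondary descriptive endpoint. The primary analysis is not touched, and the data needed are collected. It should be corrected, but it is not a threat to the study's main conclusion.

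**What to change.** In SAP 7.6, keep the split by entry into the prospective period and add a Visit 1 summary of NT-proBNP in the Enrolled Set by clinical stability (yes/no): n, mean, SD, median, minimum and maximum, and frequencies in categories that include below 600 pg/ml. Add the same below-600 category to the existing Enrolled Set table. If the sponsor prefers not to produce the display, list the omission in section 7.13 with a reason.

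Optionally, show stable at or above 600, stable below 600 and not stable as three groups, for NT-proBNP and for Visit 1 adherence in 7.4.2. This would help interpretation, but the protocol does not require it.

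The cost is a sentence in the SAP and one extra table. Stability and NT-proBNP are both recorded at Visit 1 for every enrolled patient under the assessment schedule, so no new data are needed.
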